## 10 VISIT PROCEDURES

### 10.1 Screening

The Schedule of Assessments to be performed during the study are detailed in **Table 1 - Table 4**

#### 10.1.1 Subject Screening

Investigators will maintain a screening log of all potential study subjects. This log will include limited information about the potential subject (screening identification (ID), date of consent, initials, date of birth, sex, race and ethnicity), the outcome of the screening process, and the date of the outcome. Investigators will provide information about the study to subjects who appear to meet the criteria for participation in the study.

After obtaining informed consent, the full assessment of eligibility will be conducted according to the Schedule of Assessments in **Table 1** or **Table 2**. Results of tests performed that would ordinarily be performed according to the standard of medical care, may be used for screening purposes if obtained within the screening period. Once the subject has fulfilled all entry criteria, a subject ID will be assigned.

Subjects who do not meet eligibility criteria may be re-screened at the discretion of the sponsor. Any subject who is re-screened will be assigned a new screening ID number and will be required to repeat all screening procedures unless approved in advance by the sponsor.

For those subjects who are screened for the study but are considered ineligible or are never entered into the study (i.e., do not receive study medication), the following eCRF data will be collected: date of informed consent, demographic information, AEs, and reason for non-participation (e.g., inclusion and/or exclusion criteria not met, withdrawal of consent, etc.).

### 10.2 Cycle 1

All study assessments will be conducted in accordance with the Schedule of Assessments in **Table 1 - Table 4**, as applicable to the study part assignment. During visits when multiple PK

samples are collected, the following “priority order” will be in effect when more than 1 assessment is required at a particular time point:

- PK blood sampling will take priority over all study procedures except ASN002 dose administration. Pre-dose samples should be obtained immediately (within 1 hour) prior to dose administration.
- Safety assessments (e.g., vital signs, 12-lead ECG, AE questioning) may be performed within 15 minutes of the protocol specified time point.

#### 10.2.1 Day 1

The subject should arrive at the investigational site after an overnight fast of at least 8 hours. The investigator will confirm the subject’s eligibility for the study and ensure the subject’s condition has not changed since the screening assessments. The subject will have the following procedures performed on Day 1:

- Obtain hematology, serum chemistry, liver function tests, urinalysis, and pregnancy test (if applicable) if not done within 72 hours prior to Day 1 (**Table 10**);
- Perform physical examination within 72 hours of Day 1 (Section **12.10**), including ECOG PS and measurement of the spleen by manual palpation in subjects with MF;
- Review study entry criteria to confirm eligibility (Section **9**);
- Obtain baseline MPN-SAF form completed for MF subjects only;
- Obtain pre-dose PK/PD samples (Section **13.1**), ECG tracing (Section **12.9**), and vital signs including weight (Section **12.8**) according to the schedule in **Table 3** or **Table 4**, as applicable;
- If dosing is to occur in the presence of food, a light meal will be administered prior to dosing. ASN002 should be administered within 15 minutes of consumption of the light meal.
- Administer assigned dose of ASN002 with approximately 240 mL of water;
- Obtain post-dose PK/PD samples, ECG tracings, and vital signs according to the schedule in **Table 3** or **Table 4**, as applicable;
- Observe for adverse events;
- Record any changes in concomitant medications since the last visit

#### 10.2.2 Day 2

- Obtain a 1 PK sample (Section **13.1**), ECG tracing (Section **12.9**), and vital signs (Section **12.8**) according to the schedule in **Table 3** or **Table 4** (as applicable).
- Assess for AEs and changes to concomitant medications.
- If dosing is to occur in the presence of food, a light meal will be administered prior to dosing. ASN002 should be administered within 15 minutes of consumption of the light meal.
- Dispense ASN002 for dosing at home, if the subject is assigned to a bid dosing regimen.

- Hold dosing if the subject is participating in a QD cohort.
- Provide Diary card to the subject, and provide instructions for completion

#### 10.2.3 Day 3

##### **For subjects in the QD dosing cohorts only**

The subject will arrive at the study site in the morning in a fasted state prior to taking the study drug.

- Obtain a pre-dose PK sample (Section 13.1), ECG tracing (Section 12.9), and vital signs (Section 12.8) according to the schedule in **Table 3**; prior to study drug administration;
- If dosing is to occur in the presence of food, a light meal will be administered prior to dosing. ASN002 should be administered within 15 minutes of consumption of the light meal.
- Administer assigned dose of ASN002 with approximately 240 mL of water after PK sample is collected;
- Dispense ASN002 for dosing at home;
- Fast may be broken approximately 2 hours after dosing;
- Assess for AEs and changes to concomitant medications.

#### 10.2.4 Day 4, and 11 ( $\pm$ 1 day)

Part A only

- Obtain blood sample for liver function tests (**Table 10**);
- Assess for AEs and changes to concomitant medications.

#### 10.2.5 Day 8 ( $\pm$ 1 day)

The subject will arrive at the study site in the morning in a fasted state prior to taking the study drug.

Part A

- Obtain a trough level PK sample and PD sample prior to study drug administration (**Table 3** or **Table 4**, as applicable);
- Obtain clinical laboratory assessments as described in **Table 1**, or **Table 2** (as applicable) and **Table 10**; Perform ECG; Obtain vital signs (Section 12.8);
- Assess ASN002 treatment compliance (Section 10.7);

- Observe for adverse events, and record any changes in concomitant medications since the last visit;
- If dosing is to occur in the presence of food, a light meal will be administered prior to dosing. ASN002 should be administered within 15 minutes of consumption of the light meal.
- Administer ASN002 with approximately 240 mL of water;
- Dispense ASN002 for dosing at home, if indicated;
- Fast may be broken approximately 2 hours after dosing for subjects who remain fasted.

Part B assessments

- Obtain MPN-SAF form completed for MF subjects only;
- Vital signs and ECG are not required on Day 8, 15 and 22 in Part B
- Treatment compliance occurs at the end of Cycle 1

#### 10.2.6 Day 15 ( $\pm 1$ day)

Subjects will arrive at the study site in the morning of Day 15 after an overnight fast of at least 8 hours. The following procedures will be performed.

- Obtain PK/PD samples according to Section **13.1** and **Table 3** or **Table 4**, as applicable;
- Perform physical examination (Section **12.10**);
- Obtain clinical laboratory assessments as described in **Table 1**, **Table 2**, and **Table 10**
- Obtain vital signs according to **Table 3**;
- Obtain ECG tracing according to **Table 3**;
- Assess ASN002 treatment compliance;
- Observe for adverse events, and record any changes in concomitant medications since the last visit;
- If dosing is to occur in the presence of food, a light meal will be administered prior to dosing. ASN002 should be administered within 15 minutes of consumption of the light meal.
- Administer ASN002 with approximately 240 mL of water;
- Dispense ASN002 for dosing at home, if indicated;
- Fast may be broken approximately 2 hours after dosing.

Part B assessments

- Obtain MPN-SAF form completed for MF subjects only

#### 10.2.7 Day 16 ( $\pm 1$ day)

**For subjects in the QD dosing cohorts only**

- Obtain a trough level PK sample (Section **13.1**), ECG tracing (Section **12.9**), and vital signs (Section **12.8**) according to the schedule in **Table 3**;
- If dosing is to occur in the presence of food, a light meal will be administered prior to dosing. ASN002 should be administered within 15 minutes of consumption of the light meal.
- Administer assigned dose of ASN002 with approximately 240 mL of water;
- Fast may be broken approximately 2 hours after dosing;
- Assess for AEs and changes to concomitant medications.

#### 10.2.8 Day 22 ( $\pm 1$ day)

The subject should arrive at the study site in the morning of Day 22 in a fasted state of at least 2 hours. The following procedures will be performed.

- Obtain a trough level PK sample prior to study drug administration;
- Obtain clinical laboratory assessments as described in **Table 1** or **Table 2** (as applicable) and **Table 10**;
- Obtain vital signs (Section **12.8**);
- Perform ECG
- Assess ASN002 treatment compliance (Section **10.7**);
- Observe for adverse events, and record any changes in concomitant medications since the last visit;
- If dosing is to occur in the presence of food, a light meal will be administered prior to dosing. ASN002 should be administered within 15 minutes of consumption of the light meal.
- Administer ASN002 with approximately 240 mL of water;
- Dispense ASN002 for dosing at home;
- Fast may be broken approximately 2 hours after dosing.

#### Part B assessments

- The MPN-SAF form (completed for MF subjects only) may be completed at home if the Day 22 laboratory assessments are not performed. Day 22 laboratory assessments may be omitted.

#### 10.2.9 Day 28

Day 28 is considered the end of Cycle 1 and the DLT assessment period. No site procedures are scheduled for Day 28. The subject should return to the study site the following day for the beginning of the next cycle. All scheduled follow up assessments must be completed prior to the initiation of subsequent ASN002 dosing.

### **10.3 Subsequent Cycles ( $\pm 3$ days)**

#### **10.3.1 Day 1**

- Perform clinical laboratory assessments according to **Table 1** or **Table 2** (as applicable) and **Table 10**, if not performed within 3 days of Day 1;
- Review disease status, if an assessment was performed (Section **11.1.1**);
- Perform physical examination (Section **12.10**) including vital signs, weight, ECOG PS. Determine if the subject should continue ASN002;
- Obtain pre-dose PK/PD sample (Section **14.1**) and **Table 3** or **Table 4**, as applicable);
- Assess ASN002 treatment compliance (Section **10.7**);
- Observe for adverse events, and record any changes in concomitant medications since the last visit;
- Dispense additional ASN002 and subject diary.

#### Part B assessments

- Obtain MPN-SAF form completed weekly for MF subjects only
- Spleen length should be assessed by manual palpation every 4 weeks for the first 24 weeks and every 12 weeks thereafter of the study (MF subjects only);

#### **10.3.2 Day 15 ( $\pm 2$ days)**

- Obtain clinical laboratory assessments as described in **Table 1** and **Table 10**
- Obtain vital signs (Section **12.8**);
- Obtain PK sample as specified in **Table 4**
- Observe for adverse events, and record any changes in concomitant medications since the last visit;
- Schedule radiographic evaluation of the subject's disease status to be conducted and evaluated prior to the end of the cycle, if appropriate;
  - For DLBCL, MCL, FL, and PTCL schedule every 12 weeks (end of Cycle 3, 6, 9, etc.).
  - For advanced solid malignancies schedule every 8 weeks (end of Cycle 2, 4, 6, etc.) for the first 24 weeks, and then every 12 weeks thereafter.
  - For MF schedule MRI (preferred) or CT of abdomen on week 24
  - For CLL schedule every 8 weeks for the initial 24 weeks and every 12 weeks thereafter (CT scan for chest/abdomen/pelvis recommended if previously abnormal and otherwise with a CR).
- Schedule a bone marrow aspirate and biopsy for CLL subjects in case of CR or cytopenias of uncertain origin.
- Obtain MPN-SAF form completed weekly for MF subjects only

## **10.4 End of Treatment**

The following assessments should be performed within 1 week of last dose of ASN002.

- Perform physical examination (Section **12.10**);
- Obtain vital signs, including weight (Section **12.8**);
- Obtain ECOG performance status (**Appendix B**);
- Obtain ECG (Section **12.9**); Perform clinical laboratory tests **Table 1** or **Table 2** (As applicable) and **Table 10**, including pregnancy test if applicable;
- Observe for adverse events, and record any changes in concomitant medications since the last visit;
- Perform disease assessment (Section **11.1.1**);
- Assess medication compliance (Section **10.7**);
- Obtain all unused medication for reconciliation and destruction.
- Obtain MPN-SAF form completed weekly for MF subjects only
- Obtain PK samples (Part B only, **Table 2**)

## **10.5 30-Day Follow-up**

The following assessments should be performed at the follow-up visit.

- Perform physical examination (Section **12.10**);
- Obtain vital signs, including weight (Section **12.8**);
- Perform clinical laboratory tests (**Table 10**);
- Follow up on all AEs ongoing at the End of Treatment visit.

## **10.6 Prior and Concomitant Medications**

Any concomitant therapy with the exceptions noted in Section **10.6.1** that are considered necessary for the subject's welfare may be given at the discretion of the investigator. The investigator will authorize the therapy after consideration of the clinical situation, the potential for masking symptoms of a more significant underlying event, and whether the use of the therapy will compromise the outcome or validity of the study.

Any concomitant therapy used while the subject is in the study must be recorded in the source documents and eCRF. The medication name, dosage, date, and indication for use must be recorded. The Medical Monitor should be notified in advance of (or as soon as possible after) any instances in which prohibited therapies are or need to be administered.

Any changes to ongoing concomitant medications or the addition of new medications must be recorded in the source documents and eCRF.

Upon entering the study, each subject will be instructed to report the use of any medication to the investigator. Subjects will also be instructed about the importance of not taking any medication (including over-the-counter medications) without consulting the investigator.

#### 10.6.1 Prohibited Medications

The following medications will be prohibited during the study:

- Chemotherapy, radiotherapy, immunotherapy, or investigational treatments are not allowed with concomitant use of ASN002;
- Use of localized palliative radiation for pre-existing lesions for pain control may be approved after discussion with the sponsor. The radiation field must not include any target or non-target lesions, and progressive disease must be ruled out as the underlying requirement for palliative radiotherapy.
- Therapeutic doses of anticoagulants.

#### 10.6.2 Concomitant Use of Drugs that may Affect Gastric pH

The use of antacids and H2 antagonists should be considered in place of proton pump inhibitors in patients receiving ASN002. Aluminum, magnesium, or calcium-based antacids and H2-antagonists should be taken in a window of 2-10 hours after administration of the actual dose of ASN002. Refer to **Table 8** for examples of concomitant medication that may affect gastric pH.

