**Table 8: Examples of H2 antagonists, and Proton Pump Inhibitors**

H2 antagonists	Proton Pump Inhibitors	Antacids
cimetidine	esomeprazole	Aluminum-based antacids
omeprazole	lansoprazole	Magnesium-based antacids
nizatidine	pantoprazole	Calcium-based antacids
ranitidine	rabeprazole	

The examples provided are not an exhaustive list of possible drugs that may affect gastric pH.

The investigator is responsible for assessing all concomitant medications that may have effects on gastric pH.

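### Protocol Table 8 lists omeprazole, a proton pump inhibitor, as an H2 antagonist, so it conflicts with the substitution advice in Section 10.6.2 that it is meant to support

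*Protocol*

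**What the plan says.** Protocol Section 10.6.2 covers drugs that may change gastric pH. Its advice is: "The use of antacids and H2 antagonists should be considered in place of proton pump inhibitors in patients receiving ASN002". For timing it says that antacids of the aluminum, magnesium or calcium type and "H2-antagonists should be taken in a window of 2-10 hours after administration of the actual dose of ASN002". It states no window for proton pump inhibitors. It then points the reader to Table 8 "for examples of concomitant medication that may affect gastric pH".

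Table 8 has three columns, headed "H2 antagonists Proton Pump Inhibitors Antacids". Its second row reads "omeprazole lansoprazole Magnesium-based antacids", so omeprazole stands under H2 antagonists. The proton pump inhibitor column contains "esomeprazole" and three other drugs with the same name ending.

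Two notes follow the table. One says that the list is not complete. The other reads: "The investigator is responsible for assessing all concomitant medications that may have effects on gastric pH".

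Section 10.6.1, on prohibited medications, does not name proton pump inhibitors. Section 10.6 leaves other concomitant therapy to the investigator's discretion.

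**The concern.** Section 10.6.2 gives the two drug classes opposite roles. One is the class that sites are asked to consider replacing, and the other is a suggested replacement with its own timing. The column in which a drug is printed therefore decides how a site handles it. According to the Summary of Changes, the allowance for H2 antagonists within the 2-10 hour window came in with the current amendment, so column membership now matters in practice.

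If omeprazole is in the wrong column, a site that checks a subject's medication against the table gets the wrong answer for that drug. What could be at stake is pharmacokinetic (PK) information. PK is the secondary objective in both parts, and Part A looks at exposure by dose and by fed or fasted state in cohorts of 3 or 6. In cohorts of that size one subject is 1/3 = 33% or 1/6 = 17% of a dose level.

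**Working it through.** The plan has no figure on this point to reproduce, and no formula applies. The check sets the table against the section.

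**1. Is the entry a fault of text extraction?** Read against the three headers, the rows of Table 8 are:

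| H2 antagonists | Proton pump inhibitors | Antacids |
|---|---|---|
| cimetidine | esomeprazole | aluminum-based |
| omeprazole | lansoprazole | magnesium-based |
| nizatidine | pantoprazole | calcium-based |
| ranitidine | rabeprazole | (empty) |

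A shifted row would also have moved lansoprazole or the magnesium-based antacids, and neither has moved. The entry is in the protocol as written.

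**2. How many entries are wrong?** In the H2-antagonist column 1 of 4 drugs (omeprazole) is a proton pump inhibitor. In the proton pump inhibitor column 0 of 4 are misplaced. So 4 + 4 - 1 = 7 of the 8 named drugs are in the right class. The table itself points to the slip, because omeprazole is the only drug with its name ending outside the proton pump inhibitor column.

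**3. What changes when Section 10.6.2 is applied to the entry?**

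| | Omeprazole as printed | Omeprazole under its own class |
|---|---|---|
| Role in the advice | suggested substitute | drug for which a substitute is to be considered |
| Timing window | 2-10 hours after the dose | none stated |
| Prohibited by Section 10.6.1 | no | no |

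The first two lines change and the third does not. The error therefore reverses the advice and attaches a window that the section does not give to that class. It does not change whether the drug may be used.

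**4. Does anything else correct it?** Protocol Sections 10.6, 10.6.1 and 15.5.1 and SAP Section 10.3 deal with concomitant medication. None of them restates or corrects the class of omeprazole.

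**5. Does it reach the analysis?** Protocol Section 15.5.1 classifies medications with WHO Drug. SAP Section 10.3 reports them by ATC category and preferred name. Coding follows the recorded drug name, and nothing says that Table 8 feeds into it. The Part B test in SAP Section 4 (14 per cohort, null response rate 0.05) does not depend on the table either.

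**6. Can the effect on exposure be sized?** No. The documents give no figure and no direction for a gastric-pH effect on ASN002. The only exposure change they quote for a condition of intake is the rise of about 80% with a low-fat meal (Protocol Sections 6.4.2 and 6.4.5). That is not an estimate of the effect of acid suppression.

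**The case against.** The strongest reply is that the slip has little force in practice. The advice is worded as something to consider. Proton pump inhibitors are not prohibited, so a subject on omeprazole could stay on it even if the table were right. Under Section 10.6 the investigator authorizes each therapy and weighs whether it would compromise the study, and subjects are told not to take any medication without consulting the investigator. The note below Table 8 repeats the investigator's responsibility for gastric-pH drugs. ASN002 concentrations are also measured in all subjects in both parts, so altered exposure would not be invisible.

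All of this stands, and it limits the consequence. It also answers a stronger reading: a reader might infer that the error lets in a drug that would otherwise be barred, or hides a protocol deviation. The documents do not support that. Omeprazole would not be a listed prohibited medication under either classification.

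The reply does not remove the error. The note that the list is incomplete covers drugs left out, not drugs put in the wrong class. The investigator's duty to assess is no cure when the table is the aid supplied for that assessment.

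**Conclusion.** The point holds as an internal inconsistency: Table 8 and Section 10.6.2 contradict each other for one drug and must be reconciled. Because the section relies on the table, this is an operational error and not just a typing slip. Its effect is unquantified and probably minor. No endpoint definition, error rate, power or sample size depends on it.

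The conclusion rests on the standard pharmacological class of omeprazole, which the table's own grouping of the related drugs supports, and on sites using Table 8 as Section 10.6.2 directs. The documents do not say how many subjects take omeprazole.

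A reader might go on to infer that affected subjects had lower ASN002 exposure, in effect received a lower dose, or lost a chance of response in Part B. With neither size nor direction given for a pH effect, any such figure would be pure assumption. Nor is there a basis for asking that omeprazole be recoded, since coding does not use Table 8. A request to add acid-suppressant class to the population PK model cannot be judged, because that plan is a separate document (Protocol Section 15.7.1, SAP Section 11.2) and is not available here.

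**What to change.** Correct the drug-class entry for omeprazole in Table 8 so that the table and Section 10.6.2 agree, and notify sites of the correction. The cost is one table cell and a short site memo. The SAP, the medication coding and the sample size stay as they are. This corrects a classification only: whether and when acid-suppressing drugs may be taken with ASN002 remains a clinical matter for the sponsor, and no change to that is proposed.

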**Table 8: Examples of H2 antagonists, and Proton Pump Inhibitors**

H2 antagonists	Proton Pump Inhibitors	Antacids
cimetidine	esomeprazole	Aluminum-based antacids
omeprazole	lansoprazole	Magnesium-based antacids
nizatidine	pantoprazole	Calcium-based antacids
ranitidine	rabeprazole	

The examples provided are not an exhaustive list of possible drugs that may affect gastric pH.

The investigator is responsible for assessing all concomitant medications that may have effects on gastric pH.

